HIV	Human Immunodeficiency Virus
ISMS	Institute of Social and Medical Studies
KI	Key informant interviews
MI	Myocardial infarction
NIDA	National Institute on Drug Abuse
NIH	National Institutes of Health
NRT	Nicotine replacement therapy
NYU	New York University
OPC	Outpatient clinic
OTC	Over the counter
PHI	Protected health information
PI	Principal investigator
PLWH	People living with HIV
QC	Quality control
RA	Research assistant
RCT	Randomized controlled trial
SAC	Scientific Advisory Committee
SAE	Serious adverse event
SAP	Statistical and analytic plans
SC	Standard care
SoM	School of Medicine
TUT	Tobacco use Treatment
UP	Unreported problem
VHW	Village health worker
WHO	World Health Organization

PROTOCOL SUMMARY

Title	Implementation of tobacco use treatment in HIV clinics in Vietnam
Brief Summary	The primary objective of this study is to conduct a 3-arm randomized controlled trial (RCT) that compares the effectiveness of three multi-component interventions that are embedded in HIV outpatient clinics (OPCs): 1)3As+Referral (Standard Care (SC)): Ask about tobacco use, Advise to quit, Assist with brief counseling and Refer to Viet Nam's national Quitline; 2) AAA+ +Counsel (Counsel=6-session cessation counseling intervention adapted for patients living with HIV/AIDS (PLWH) and delivered by a trained, onsite nurse; and 3) AAA+Counsel+N (N=nicotine replacement therapy (NRT)). The main outcome is biochemically validated 6-months smoking abstinence. We will recruit and randomize 672 patients across 13 outpatient clinics (OPCs) (48 per site, 16 per arm). We will also recruit 75-nonsmokers to participate in a single survey to assess food safety. Therefore, the total sample = 747 patients.
Phase	Phase 3
Objectives	
The primary objective of this study is to conduct a 3-arm RCT that compares the effectiveness of three multi-component interventions to increase smoking abstinence among PLWH.
 
The secondary objective is to assess factors (health care setting, provider, and patient level factors) that may influence tobacco cessation, and sustainability of the interventions tested.
 
The primary objective of the supplement is to examine the difference in household food insecurity among people living with HIV and the relationship between food insecurity and tobacco use in Vietnam.

Methodology	The is a 3-arm unblinded RCT
Endpoint	The primary endpoint is carbon monoxide confirmed smoking abstinence at 6 months.
Study Duration	Five years

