Participant Duration	Patients and providers will be enrolled for 2 years
Duration of IP administration	Nicotine gum (for those randomized to Arm 3 in the RCT) will be given for 6 weeks.
Population	We are recruiting tobacco users who are patients at one of the 13 participating OPCs. All patients are Vietnamese. We will recruit women and men. For the research supplement (AIM 4) we will recruit non-smokers from the 13 OPCs.
Study Sites	13 HIV outpatient clinics in Hanoi
Number of participants	941 (includes providers and patient participants)
Description of Study Agent/Procedure	The intervention being tested in the RCT is behavioral only in ARM 1 and 2 and in ARM 3 patients will also receive nicotine gum for daily use for 6 weeks.
Reference Therapy	NA. There is no placebo. This is an effectiveness study using an over the counter drug.
Key Procedures	NA

Statistical Analysis	The primary analytic approach used to compare study arms is conditional logistic regression. This fixed effects approach was chosen as primary because of the modest number of sites and the fact that they are not very heterogeneous. Because some methodologists have advocated mixed effects models even when the number of sites is small, we will use a multilevel logistic regression model as an alternative, sensitivity analysis approach. In an intent-to-treat analysis of all study entrants, conditional logistic regression analysis will compare study arms on the primary outcome, 7-day point prevalence CO confirmed (<10 ppm) tobacco abstinence captured at 6-month follow up. The outcome will be regressed on indicator variables for study arm and OPC site will be the stratification variable. Pairwise comparisons of arms will be undertaken to determine which arms are significantly different. Pairwise comparisons will be adjusted for multiple comparisons using the Tukey method. Effect magnitudes will be based on odds ratios for the pairwise comparisons, which will be calculated by exponentiating the coefficients for pairwise contrasts. Secondary cessation outcomes, HIV-related outcomes, hypothesized mediators (e.g., risk perceptions, self-efficacy), and the food insecurity outcomes also will be analyzed with conditional logistic regression, or a different fixed effects regression appropriate to the type of outcome variable.
----------------------	---

SCHEMATIC OF DESIGN. This research has three phases. For Aim 1 we will conduct a formative

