assessment to inform further modifications to the intervention components. Participants in Aim 1 will be patients of the outpatient clinics (OPC) or health care providers who work there. Patients who use tobacco will be asked to participate in individual interviews (n=24). We will conduct key informant interviews with health care providers from 3 OPCs (n=28) to adapt the intervention to the OPC clinical context. We will then conduct a pilot test of ARM 1 and 3 in one OPC with 16 patients. The recruitment and enrollment process will be the same as described for Aim 2. For Aim 2 we will conduct a three-arm randomized controlled trial (RCT) to compare the effectiveness of three interventions aimed at increasing tobacco cessation rates among people living with HIV/AIDS (PLWH). Patients (n=672) will be recruited and enrolled from the 13 OPCs. All enrolled patients will complete a baseline survey in person. This survey will be administered once eligibility is established and consent is obtained. The consent and survey will last 30 minutes. Follow up surveys will occur at 3- and 6-months after enrollment. Follow up surveys will be conducted by telephone. At 6-months follow up, patients who report smoking abstinence will be asked to come in person to the OPC and will complete a carbon monoxide test to validate self-report. We will conduct baseline and 12-month surveys with all health care providers in the study sites in person (n=98). For Aim 3 we will conduct 12-month post intervention interviews and an 18-month survey to assess factors associated with implementation effectiveness and potential for sustainability. For Aim 4 we will enroll 75 more patients who are non-smokers for a total of (n=747) patients and assess the relationship between food insecurity and tobacco use among PLWH (75 smokers and 75 non-smokers), which includes administering the Household Food Insecurity Access Scale (HFIAS) survey to patients at baseline and 6-months.

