AIM 4: We will collect data on food insecurity from 75 non-smokers and 672 smokers at baseline and 6-months.

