5.4.3. AIM 3. At the time of enrollment in AIM 2, providers will also be asked to participate in the KIs 12 months after the intervention period. Consent will be obtained at the time they enroll in AIM 2. For the 18-month sustainability survey, written consent will be obtained at the time they are approached to participate in the survey.

5.4.4. Aim 4. We will enroll 75 patients who are non-smokers using the same strategy as AIM 2.

5.5 DURATION OF STUDY PARTICIPATION. Patient individual interview participants will be asked to participate for the single session. Providers and patients who participate in the RCT will be enrolled for 2 years. Patients who are non-smokers (n=75) participating in the diversity supplement study will be enrolled for six months.

5.6 TOTAL NUMBER OF PARTICIPANTS AND SITES. For Aim 1, we will conduct 24 patient interviews and 28 provider interviews across 3 OPCs. We will recruit 16 patients in the one OPC that will serve as the pilot study site. For Aim 2 we include 672 patients (48 patients per site, 16 per arm). Surveys will be conducted, at baseline, with all health care providers in the 13 sites in person (n=98). For Aim 3, we will repeat surveys and KIs among the 48 providers with 2 health care providers per site, 13 sites, (n=28) at 12-months post intervention, and will separately conduct a sustainability survey at 18-months with the same providers. For Aim 4, we will include 75 patients (at least 5 patients per site).

5.7 PARTICIPANT WITHDRAWALS OR TERMINATION.

5.7.1. Reason for withdrawal. This is a minimal risk study so we do not expect participants to withdraw for a safety-related issue. However, participants (providers and patients) are free to

withdraw from participation in the study at any time upon request without any impact on their ability to continue to receive care or to be employed.

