7.1.3 Study visits

AIM 1 Patients: The first and final visit for patients in AIM 1 is the interview. Patients enrolled in the AIM 1 pilot study will complete the same study visits as described below in Aim 2.

AIM 1-3 Providers: Provider visits include in person KIs for Aim 1 (n=28). For Aim 2 providers will be asked to complete a baseline survey (n=98) and KIs (n=28) across the 13 study OPCs. For AIM 3 we will repeat the survey and KIs at 12 months, and separately conduct a sustainability survey at 18 months.

AIM 2 RCT and AIM 4: Patients will be asked to complete a baseline, 3-, and 6-month survey. The baseline survey will take place in person. All other surveys will be conducted by telephone, 3 and 6-months. At 6-months follow up patients who report smoking abstinence will be asked to come in person to the OPC and will complete a carbon monoxide test at the OPC to validate self-report.

7.1.4. Methods and Procedures.

AIM 1: Patient Interviews. Experienced interviewers from our partnering institution in Vietnam (i.e., Institute for Social and Medical Studies, ISMS) will conduct these interviews (n=24). The number of interviews will depend on reaching saturation.

AIM 1-3: Health care provider surveys and interviews. All interviews and surveys will be administered by experienced ISMS staff. The interviews will be digitally recorded, transcribed and translated and stored as described above. We will not conduct the interviews if participants refuse to have the interview recorded. Surveys are administered using REDCap on iPads at baseline and 12 months and 18 months post intervention.

AIM 2 RCT and AIM 4: All patient surveys are administered using REDCap. The baseline patient survey is conducted in person at the time of enrollment. All other surveys will be conducted by telephone, 3- and 6- months. At 6-months follow up patients who report smoking abstinence will be asked to come in person to the OPC and will complete a carbon monoxide test at the OPC to validate self-report. The CO test involves the patient blowing through a small cardboard tube into a small handheld monitor which measures the amount of CO expired. A positive test (i.e., still smoking) will be defined as >10ppm. The CO test visit will take about 20 minutes and the findings will be recorded in REDCap.

7.1.5. Withdrawal/Early termination visit. The clinical site, patients and providers may withdraw from the study at any time.

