AIM 4: When comparing smokers and non-smokers at baseline on the HFIAS, power is 80% to detect a standardized mean difference of $d=0.46$ (about half a standard deviation, a difference of 3 HFIAS points assuming a standard deviation of 6) given the proposed sample size of $n= 150$ (75 smokers and 75 non-smokers). When estimating the relation between income and HFIAS, power is 80% to detect a squared multiple correlation of $R^2=.05$ given the proposed sample size of $n=150$. When estimating the impact of smoking cessation on HFIAS at the 6-month follow-up, power is 80% to detect a standardized mean difference of $d=0.89$ (about nine tenths of a standard deviation, a difference of 6 HFIAS points) given the proposed sample size of $n=75$ smokers at baseline and assuming at least 16% of smokers ($n=12$) achieve cessation.

9.2 STATISTICAL HYPOTHESIS. The primary hypothesis is that more intensive counseling delivered by a trained nurse (ARM 2) will be more effective than provider brief counseling plus Quitline counseling (ARM 1) in increasing smoking abstinence. We further hypothesize that adding nicotine replacement therapy to the more intensive counseling will increase cessation rates more than the intensive counseling alone (ARM 3).

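### Aim 4 is sized on 75 smokers, but section 4.1 collects food-insecurity data from 672, and no rule says which smokers are analysed

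*Combined protocol and SAP*

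**What the plan says.** Section 4.1, under Aim 4, is explicit about who supplies the data: "We will collect data on food insecurity from 75 non-smokers and 672 smokers at baseline and 6-months".

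The Schematic of Design describes the same aim on a smaller set. It says the study will "assess the relationship between food insecurity and tobacco use among PLWH (75 smokers and 75 non-smokers"), with the Household Food Insecurity Access Scale (HFIAS) given at baseline and 6 months.

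Section 9.1, under Aim 4, bases all three of its power statements on the smaller set:

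- Baseline, smokers v non-smokers: n=150 (75 and 75), d=0.46, described as 3 HFIAS points at an SD of 6.
- Income and HFIAS: n=150, R-squared 0.05.
- Cessation and HFIAS at 6 months: d=0.89, "given the proposed sample size of $n=75$ smokers at baseline and assuming at least 16% of smokers ($n=12$) achieve cessation".

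The Aim 4 recruitment and sample-size text (sections 5.4.4, 5.6 and 7.1.1) covers only the 75 non-smokers. Section 7.1.3 gives the RCT and Aim 4 patients one shared schedule: "Patients will be asked to complete a baseline, 3-, and 6-month survey".

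**The concern.** The two descriptions cannot both define the Aim 4 analysis set, and both stand in the current text. If all RCT smokers answer the HFIAS, section 9.1 plans on about a ninth of the available smokers (75 of 672). If only 75 are meant, section 4.1 is wrong and a selection rule is missing.

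Two things are at stake. The first is precision. The cessation part of the supplement's third objective (section 3) is planned on 12 quitters, when at the same 16% quit rate section 4.1 would measure about 108 before loss. The second is prespecification. Without a stated set or selection rule, the choice of smokers could be made after the data are seen.

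**Working it through.** **Inputs from the documents.** 75 or 672 smokers and 75 non-smokers; 16% quitting; 80% power; HFIAS SD 6 (section 9.1, Aim 4; section 4.1). The plan also gives 13 sites with 48 smokers each, which is 13 x 48 = 624 and not 672, so both totals are carried.

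**Assumptions.** Aim 4 states no significance level. Two-sided 5% is assumed because it reproduces the stated values; one-sided 5% gives 0.41 and 0.79 in place of 0.46 and 0.89. The documents give no loss rate for these data, so 20% is an assumption. The baseline SD of 6 is assumed to hold at 6 months.

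**Formula.** For groups of n1 and n2, d = (1.960 + 0.842) x sqrt(1/n1 + 1/n2). The results below are the noncentral-t equivalents, which are slightly larger in small groups. All are unadjusted.

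**Step 1: reproduce the plan.**

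- 75 v 75: d = 0.460 (stated 0.46).
- 12 v 63: the formula gives 2.802 x sqrt(1/12 + 1/63) = 0.882, and noncentral t gives 0.894 (stated 0.89).
- R-squared, one predictor, n=150: 0.050 (stated 0.05).

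The section 9.1 figures are therefore correct for 75 smokers, and the 6-month figure keeps all 75.

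**Step 2: use the smokers named in section 4.1.** At 16% quitting, 0.16 x 672 = 107.5 quitters and 564.5 non-quitters; 0.16 x 624 = 99.8 and 524.2.

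| Comparison | 75 smokers | 672 smokers | 624 smokers |
|---|---|---|---|
| Baseline, smokers v 75 non-smokers | d=0.46 | d=0.34 (2.05 points) | d=0.34 |
| Income, R-squared (one predictor) | 0.050 (n=150) | 0.010 (n=747) | 0.011 (n=699) |
| 6-month cessation, no loss | d=0.89 | d=0.30 (1.8 points) | d=0.31 |
| 6-month cessation, 20% loss equal in both groups | d=1.00 (9.6 v 50.4) | d=0.33 (86.0 v 451.6; 2.0 points) | d=0.34 (79.9 v 419.3) |
| 6-month cessation, 20% loss, all quitters retained | d=0.92 (12 v 48) | d=0.30 (107.5 v 430.1) | not run |

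**Step 3: sensitivity, 672 smokers.**

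- Equal loss of 5%, 10% and 30% gives d = 0.30, 0.31 and 0.35 at 16% quitting.
- At 10% quitting, d = 0.36 with no loss and 0.40 with 20% equal loss.
- At 20% quitting with no loss, d = 0.27.

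Across these ranges the detectable effect with all smokers stays below half of the stated 0.89.

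**The case against.** The strongest reply is that 75 may be a deliberate subsample or a conservative planning figure. On either view the section 9.1 power remains valid for the design it describes, and more smokers can only raise it. That stands as far as it goes. However, no section says that 75 is a subsample or a planning figure, and section 4.1 contradicts a subsample. Nor do the documents show that 672 was the intended analysis set, so the fix has to cover both readings.

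It is also fair that the gain is uneven. At baseline the 75 non-smokers limit precision, so d moves only from 0.46 to 0.34. The large gain is confined to quitters v non-quitters, where more smokers narrow the interval without removing confounding.

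The restated effects are unadjusted two-group figures, whereas the protocol summary plans a model: "and the food insecurity outcomes also will be analyzed with conditional logistic regression, or a different fixed effects regression". Section 9.1 also promises patient characteristics as covariates. The figures should therefore be labelled as unadjusted.

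Some stronger readings are tempting but not supported:

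- **That the whole third objective rests on 12 quitters.** The objective also covers reduction in tobacco use, which does not split smokers 12 v 63 and has no power statement.
- **That the plan is underpowered for 3 HFIAS points at 6 months.** The 3 points belong to the baseline smoker v non-smoker comparison. No such target is set at 6 months.
- **That "a difference of 6 HFIAS points" is an arithmetic error.** At SD 6, d=0.89 is 5.3 points, but the same paragraph gives 0.46 x 6 = 2.76 as 3 points. This is loose rounding.

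**Conclusion.** The point holds as a conflict over the Aim 4 analysis set: 672 smokers in section 4.1, 75 in the schematic and section 9.1, and no selection rule. The stated effects are arithmetically sound for 75 smokers but do not describe the data in section 4.1, and the 6-month figure allows for no loss.

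If section 4.1 holds, the detectable 6-month cessation effect is about d=0.30 with no loss, or 0.33 with 20% equal loss, instead of 0.89. This rests on 16% quitting among all smokers, an assumed two-sided 5% level, an SD of 6 at 6 months and, for the second figure, the assumed loss. If only 75 smokers are meant, a 20% loss moves the stated 0.89 to between 0.92 and 1.00.

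The sponsor should make the change, but its reach is limited. The large gain concerns the cessation part of one supplement objective, and it is precision in a non-randomised contrast. A reader should not infer that the primary endpoint or the randomised comparison is affected.

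**What to change.** **If section 4.1 is right:** state in section 9.1 and the schematic that Aim 4 analyses every enrolled smoker with HFIAS data plus the 75 non-smokers. Restate the detectable effects, labelled as unadjusted, with 80% power, two-sided 5% and SD 6:

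- baseline d about 0.34;
- income R-squared about 0.01 (one predictor);
- 6-month cessation at 16% quitting d about 0.30 (1.8 points) with no loss and 0.33 (2.0 points) with an assumed 20% equal loss, or 0.31 and 0.34 if enrolment is 624.

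**If only 75 smokers are meant:** correct section 4.1, prespecify how the 75 are selected (for example at random within site), and replace the 6-month figure with one that allows for loss. At an assumed 20% that is d about 0.92 if all 12 quitters are retained and 1.00 if loss is equal.

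**Under either reading:** state the significance level for Aim 4. Adjusting the 6-month comparison for baseline HFIAS, which is already collected, is a sensible option.

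A separate inconsistency can be settled in the same edit, though it does not affect which smokers are analysed. The protocol summary says "We will also recruit 75-nonsmokers to participate in a single survey to assess food safety", while section 5.5 says "Patients who are non-smokers (n=75) participating in the diversity supplement study will be enrolled for six months", and the schematic and sections 4.1 and 7.1.3 also carry Aim 4 follow-up to 6 months. These should be reconciled.

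The cost is wording in section 9.1, the schematic and the summary (and section 4.1 under the second reading), plus rerun power figures. No new data are needed if section 4.1 is followed.

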9.3 PLANNED INTERIM ANALYSIS

We will conduct descriptive statistics to be presented to the DSMB at the biannual meetings. This will include analysis of recruitment progress to address any barriers and to review the safety data.

10. SOURCE DOCUMENTS AND ACCESS TO SOURCE DATA/DOCUMENTS. The study case report form (CRF) is the primary data collection instrument for the study. All data requested on the CRF must be recorded. All missing data must be explained. If a space on the CRF is left blank because the procedure was not done or the question was not asked, write "N/D". If the item is not applicable to the individual case, write "N/A". All entries should be printed legibly in black ink. If any entry error has been made, to correct such an error, draw a single straight line through the incorrect entry and enter the correct data above it. All such changes must be initialed and dated. For clarification of illegible or uncertain entries, print the clarification above the item, then initial and date it. Access to study records will be limited to IRB-approved members of the study team. The investigator will permit study-related monitoring, audits, and inspections by the IRB, the sponsor, government regulatory bodies, and University compliance and quality assurance groups of all study related documents (e.g. source documents, regulatory documents, data collection instruments, study data etc.). The investigator will ensure the capability for inspections of applicable study-related facilities. Participation as an investigator in this study implies acceptance of potential inspection by government regulatory authorities and applicable University compliance and quality assurance offices.

11. QUALITY ASSURANCE AND QUALITY CONTROL (QC).

QC procedures will be implemented beginning with the data entry system and data QC checks that will be run on the database will be generated. Any missing data or data anomalies will be communicated to the site(s) for clarification/resolution. Following written Standard Operating Procedures, the monitors will verify that the clinical trial is conducted and data are generated, documented (recorded), and reported in compliance with the protocol, GCP, and the applicable regulatory requirements (e.g., Good Laboratory Practices (GLP), Good Manufacturing Practices (GMP)). The investigational site will provide direct access to all trial related sites, source data/documents, and reports for the purpose of monitoring and auditing by the sponsor, and inspection by local and regulatory authorities.

12. ETHICS/PROTECTION OF HUMAN SUBJECTS

The investigator will ensure that this study is conducted in compliance with the Declaration of Helsinki, Council for International Organizations of Medical Science (CIOMS), International Ethical Guidelines for Biomedical Research Involving Human Subjects (2002), or another country's ethical policy statement, whichever provides the most protection to human subjects.

12.1 INFORMED CONSENT PROCESS AIM 1. *Individual Interview with patients documentation of consent:* Patients will be screened by the nurse for eligibility as described above, asked to participate if they meet eligibility criteria, and given a date and time to speak to the RA. Verbal consent will be obtained prior to completing the screening questionnaire. All study related activities and study data collection will occur only AFTER a consent is obtained. We are requiring that interviews are audiotaped and therefore will let potential participants know that at the time they are screened to offer them an opportunity to decline at that time. We will again explain that interviews will be audio taped prior to beginning the interview at which time they will have another chance to opt out. We have requested a waiver of written consent and authorization. Participants will be given an information sheet that includes a number to call if they have additional questions. The interviews will take about 45-60 minutes. We will make it clear to the subjects that participation in the interviews is separate from any ongoing care they may receive in at the clinic and that participation is voluntary. We will emphasize that they are free to stop participation at any time and are free to refuse to answer specific questions in any assessment and can decline participation in any intervention activity.

Key informant interview with provider verbal consent: For the preintervention provider KIs we will obtain verbal consent at the time of the interview. We are requiring that interviews are audiotaped and therefore will let potential participants know that the time they are screened to offer them an opportunity to decline at that time. We have requested a waiver of written consent and authorization.

Pilot testing of RCT: The same process used for Aim 2 will be used to conduct screening and consenting of patients for the pilot test of ARM 1 and 3 in one OPC.

AIM 2 and AIM 3. Provider survey and KIs documentation of consent: Health care workers will be told about the study at a group meeting. It will be made clear to them that participation is voluntarily and they don't have to participate. This will be repeated at the time of the consent process. All health workers are eligible. Research staff will follow-up to contact providers and staff to make appointments for interviews and to administer the baseline and follow up surveys. Written consent will be obtained at the time of the baseline survey and interview prior to starting any data collection. Health care providers who participate in interviews and surveys will be asked to complete the survey and KIs again at 12 months post intervention. None of the research staff have any role in evaluating the employees or role in firing or hiring decisions. We will obtain written consent because of the longitudinal nature of the data collection (i.e., providers will be asked to participate in a survey at baseline and then at 12 months, in KIs at baseline and 12 months, and a sustainability survey at 18 months). Health care workers have the right to refuse to participate without any compromise to their employment or status.

AIM 2 RCT. Patient survey. A nurse who typically registers patients when they arrive at the OPC will screen all patients for tobacco use as part of that registration process. If they are a smoker the nurse will briefly describe the study and explain that those patients who are interested in participating will be screened for eligibility. Those patients who meet eligibility criteria, based on this initial screening will be introduced to the RA to complete the consent and baseline assessment procedures before their provider visit.

AIM 4. Patient survey for non-smokers. The consent process will follow the same steps as AIM 2 RCT above.

For all participants, we will emphasize that they are free to stop participation at any time and are free to refuse to answer specific questions in any assessment and can decline participation in any intervention activity. Participants will be informed that their decision to participate or decline to enroll in the study or any aspect of the study will not affect any services they receive at the clinic or their employment. Patients who smoke and decline to participate, will be offered the educational materials which include the Quitline number.

